- ^v Every 13-week in-clinic visits are no longer required and may be changed to every 26-week in-clinic visits (at the option of the investigator). Accordingly, study drug may be supplied every 13 or 26 weeks. If in-clinic visits are changed to a every 26 week frequency, a telephone contact should occur in between the 26-week in-clinic visits such that there will be a contact with the subject every 13 weeks (in-clinic visit alternating with telephone contacts). At each telephone contact, investigators should ask subjects about any foot problems and remind them about routine preventative foot care and early intervention for foot problems.

POSTTREATMENT TIME AND EVENTS SCHEDULE – SUBJECTS WHO PREMATURELY DISCONTINUE STUDY MEDICATION

Phase	Double-Blind Visit Schedule (Posttreatment)										
	- Starting at the nearest post-randomization week after the Follow-up					Contact Visit -					
Procedures and Evaluations											
Week ^a	2, 4 (TC) ^b	6	(TC) ^b	9	12	18	26	39	52	78 to end ^e	104 to end ^e
Procedures											
Vital signs, weight, Foot examination ^c		X		X	X	X	X	X	X	X	X
Provide container for urine collection for first morning void		X						X		X (foot examination only)	X
Serum creatinine		X			X	X	X	X	X		X
HbA _{1c}			X	X	X	X	X	X	X		X
Fasting serum lipids				X	X	X	X	X	X		X
First morning void urine for albumin/creatinine ratio ^d				X	X	X	X	X	X		X
Ongoing review											
Serious adverse events and adverse events of fracture	X	X	X	X	X	X	X	X	X	X	X
AHA agents after study drug discontinuation											At final visit or contact
Events in CV composite endpoint	X	X	X	X	X	X	X	X	X	X	X

^a After Week 78, on those occasions when the 26- and/or 52-week-interval visits overlap each other, the visit with the more comprehensive procedures will be followed.

^b Telephone contact (or an optional, unscheduled site visit, at the discretion of the investigator) will be made at Weeks 2, 4, and 9 to check the subject's status, including discussing the subject's diary entries and any CV events or adverse events. If a telephone contact or study visit is not possible, follow-up information may be collected via email or other electronic or non-electronic means.

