2.2.2. Secondary Hypotheses

In subjects with T2DM, with inadequate glycemic control, who have a history of or a high risk of CV disease, relative to placebo plus standard of care, canagliflozin plus standard of care at the end of the treatment period:

- improves beta-cell function (change from baseline in HOMA-B)
- reduces progression of albuminuria (ie, proportion of subjects with a ≥ 1 -step progression of albuminuria measured by the urine albumin/creatinine ratio)

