Subjects will remain on a stable regimen (medications and doses) of their current AHA regimen through Week 18 of the double-blind treatment phase, unless down-titration is required to manage or avoid hypoglycemia, or unless glycemic rescue criteria are met (refer to Section 6.2.2, Glycemic Rescue Therapy Through Week 18: Criteria and Implementation). After the AHA regimen stable period is completed at Week 18, the investigator should adjust the subject's AHA regimen so as to achieve target glycemic control, per standard diabetes care guidances, individualized as considered appropriate by the investigator. *Adjustments in the AHA regimen should be carefully implemented throughout the study to avoid events of hypoglycemia.*

Planned Meta-analyses (CANVAS and Other Canagliflozin Studies)

[figure not shown]
As described in Section 11.8, Meta-analyses to Support Regulatory Requirements, during the conduct of this study, data from CANVAS will be exported and integrated with data from other large, well-controlled, double-blind, randomized studies of canagliflozin to support meta-analysis to assess the rate of important CV events in a prespecified composite endpoint.

Study Duration

Subjects are expected to be followed for a maximum of approximately 7.25 years with the last visit for the last subject targeted to occur when at least 688 MACE events are accumulated between the CANVAS and CANVAS-R studies. All sites will be notified of the projected global trial end date (GTED) which is projected to occur prior to April 2017. The GTED is the stopping date of the study (ie, targeted date when the last subject completes last study visit), which will be announced to investigators at a time point when the actual accrual of events approaches the number of events required for the analysis; the announcement of the GTED may occur approximately 3 months prior to the GTED. Immediately after the projected GTED notification is sent, for subjects who remain on double-blind study drug, sites will be required to schedule the last on treatment visits and the 30-day off drug follow-up visits as per the Time and Events Schedule; for subjects who prematurely discontinue study drug, sites will be required to make a final contact (eg, schedule the last follow-up visit) or vital status check as soon as possible after announcement of GTED.

All visits (including the 30-day off drug follow-up visit) will need to be completed prior to the GTED.

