9.1.3. Double-Blind Treatment Phase

Day 1/Day of Randomization

Potential subjects who return for the Day 1 (baseline), who have taken $\geq 80\%$ of the scheduled single-blind placebo capsules during the run-in period, and who meet the enrollment criteria will be randomly assigned in a 1:1:1 ratio to once daily treatment with canagliflozin 100 mg, canagliflozin 300 mg, or matching placebo. Subjects will continue treatment until the study completes or the subject is prematurely withdrawn from double-blind study medication (refer to Section 10.2, Withdrawal From the Study, for reasons for withdrawal).

In addition, pharmacogenomic informed consent will be obtained (only from those subjects who agree to participate in this component).

Visits Following Randomization

Subjects will be seen in the clinic at visits or contacted by telephone as described in Section 9.1.1, Overview, and in the Time and Events Schedule. Procedures and clinical

laboratory assessments for each visit or contact are outlined in the Time and Events Schedule.

Subjects who experience nonfatal events in the CV composite endpoint (ie, nonfatal MI, nonfatal stroke) during the double-blind treatment phase will continue in the study, continuing to receive double-blind study drug and complete all assessments at all scheduled visits, as appropriate.

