Additional efficacy endpoints of interest will include the following: changes from baseline to end-of-treatment in the proinsulin/insulin ratio (in a subset of subjects), urinary albumin/creatinine ratio, and eGFR; changes from baseline to Week 18 in HbA_{1c}, FPG, systolic and diastolic blood pressure, and body weight; and percent change from baseline to Week 18 in fasting plasma lipids (triglycerides, HDL-C, LDL-C, total cholesterol, and the ratio of LDL-C to HDL-C). The eGFR will be calculated using the Modification of Diet in Renal Disease [MDRD] equation (Levey 2006).

Refer to Section 11.5, CV Outcomes and Efficacy Analyses, for the evaluation of efficacy criteria.

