11.3. Sample Size Determination

The sample size for the recruitment of the initial 4,500 subjects was based upon having a sufficient number of participants to support, in concert with the other controlled clinical trials in the canagliflozin development program, a detailed pre-approval assessment of the safety and tolerability of canagliflozin. Data from this initial cohort were exported and integrated with data from other Phase 3 well-controlled studies to support a planned pre-approval meta-analysis to demonstrate that the upper bound of the 2-sided 95% CI for the CV HR of canagliflozin relative to control in composite endpoint events (MACE and hospitalized unstable angina) was <1.8 ; the current US regulatory requirements for filing. The FDA post-marketing requirements for canagliflozin demand a subsequent estimate of CV safety that will be performed on data from CANVAS and CANVAS-R, when sufficient events have occurred to demonstrate that the upper bound of the 95% CI HR is <1.3 based on MACE (excluding hospitalized unstable angina).

The assumed per annum event rate is 2.25% and the per annum dropout rate is 5%. With an enrollment period 1.5 years, 4,500 randomized subjects were projected to contribute sufficient CV events to support the pre-approval CV meta-analysis.

The original phased recruitment strategy allowed for an interim assessment of study feasibility to demonstrate the primary hypothesis of CV benefit using the results of the interim analysis. Results from the interim analysis (conducted after approximately 2 to

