11.5.2. Major Secondary Efficacy Endpoints

The continuous secondary efficacy endpoint, change from baseline in HOMA-B will be analyzed using an analysis of covariance (ANCOVA) model with treatment (canagliflozin 100 mg, canagliflozin 300 mg or placebo) and stratification factors as fixed effects and the corresponding baseline value as a covariate. The treatment difference (each dose of canagliflozin minus placebo) in the least-squares means and the 2-sided 95% CI will be estimated based on this model. The analyses for beta-cell function will be conducted on subjects not receiving insulin at randomization and, for subjects who are started on insulin during the study, the last data point before the initiation of insulin will be included for these analyses.

The categorical secondary efficacy endpoint is the proportion of subjects with progression of albuminuria (defined as ≥ 1 step increase, ie, no albuminuria to micro- or macro-albuminuria or from micro-albuminuria to macro-albuminuria). The proportion of subjects with progression of albuminuria will be analyzed using the logistic model with treatment (canagliflozin 100 mg, canagliflozin 300 mg or placebo), and stratification factors as a fixed effect. Albuminuria will be assessed according to the categorizations defined in the National Kidney Foundation Kidney Disease Outcomes Quality Initiative Guideline #1 (KDOQI 2007): the definition of micro-albuminuria is albumin/creatinine ratio of 30 to 300 mg/g, and the definition of macro-albuminuria is albumin/creatinine ratio greater than 300 mg/g.

For the secondary endpoints of HOMA-B and proportion of subjects with progression of albuminuria, the analyses will compare the dose groups, *combined* and *individually*, relative to placebo.

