11.5.3. Multiplicity Adjustment

To ensure the family-wise Type I error rate (alpha level) in this study is at most 5%, a gatekeeping procedure will be applied in testing the primary and secondary hypotheses. The superiority of the canagliflozin combined doses over placebo in time to MACE will be tested first. If statistically significant, the procedure will proceed to test the secondary endpoints of the proportion of subjects with progression of albuminuria and HOMA-B for

each canagliflozin dose versus placebo. Details of the gatekeeping procedure will be contained in the SAP.

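### The gatekept albuminuria-progression endpoint ignores time at risk, so if it is read at each subject's own end of treatment, unequal drug stopping shifts the odds ratio without any drug effect

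*Protocol*

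**What the plan says.** Protocol 11.5.2 defines the categorical secondary endpoint as the proportion of subjects whose albuminuria category rises by at least one step, and fixes the method: "The proportion of subjects with progression of albuminuria will be analyzed using the logistic model with treatment", together with stratification factors. No assessment time and no exposure term is given there.

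The time point comes from 2.2.2, where the hypothesis concerns "canagliflozin plus standard of care at the end of the treatment period". Section 9.1.3 says when treatment ends: "Subjects will continue treatment until the study completes or the subject is prematurely withdrawn from double-blind study medication". An end-of-treatment/early withdrawal evaluation is done at that point (9.1.4). The companion continuous endpoints in 9.5 carry the same anchor: "changes from baseline to end-of-treatment in the proinsulin/insulin ratio (in a subset of subjects), urinary albumin/creatinine ratio, and eGFR". Section 3.1 gives the length: "Subjects are expected to be followed for a maximum of approximately 7.25 years".

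Under 11.5.3, once MACE is significant, "the procedure will proceed to test the secondary endpoints of the proportion of subjects with progression of albuminuria and HOMA-B" for each dose against placebo, within a family-wise error of at most 5%. MACE itself is analysed as time to first event in a Cox model (11.5.1).

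Subjects who stop drug early stay on the Posttreatment Time and Events Schedule, which lists "First morning void urine for albumin/creatinine ratio". Section 11.1 defines the mITT window as first dose to last dose plus 30 days, and leaves to the SAP which secondary endpoints use ITT and which use mITT.

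**The concern.** Progression accumulates with time. Under an end-of-treatment reading, a subject who stops drug after a few weeks and one treated for about 7 years each contribute a single yes or no. If the arms stop drug at different rates, their average time at risk differs, and the logistic model attributes the difference to treatment. The arm that stops more looks better.

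The protocol gives some reason to expect a difference: 1.1.2 reports that discontinuations due to adverse events were slightly higher on canagliflozin than on control in the development program. That direction would favour the drug. At stake is one of only two secondary endpoints for which a confirmatory claim is planned, tested for each dose.

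**Working it through.** **The plan's own figures.** The protocol gives no sample size or power for albuminuria. Its MACE power (11.3) matters here only because MACE is the gate. With 400 events and 2:1 allocation (combined doses to placebo), power = Φ(|ln HR| × √(400 × 1/3 × 2/3) − 1.96) gives 33.4%, 55.7% and 77.4% at HR 0.85, 0.80 and 0.75. The protocol states 33%, 55% and 76%, so its figures reproduce.

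**Inputs from the protocol.** 4,330 randomised 1:1:1, about 1,443 per arm; maximum follow-up about 7.25 years; enrolment 1.5 years, so potential follow-up is about 5.75 to 7.25 years; dropout 5% per year.

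**Assumptions.** T = 6 years; 92% evaluable, so 1,443 × 0.92 ≈ 1,328 per arm; constant hazards; progression hazard l = 5%, 8% or 12% per year in both arms (no drug effect); one arm stopping drug at d = 5% per year. The protocol's 5% is study dropout, borrowed here as a stopping rate because no stopping rate is given.

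**Model 1: progression counted up to the subject's own stop, with no reversal.**

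P = l/(l+d) × (1 − exp(−(l+d)T))

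Worked case, l = 8%, placebo stopping at 5%, canagliflozin at 7%:
- Placebo: 0.08/0.13 × (1 − e^−0.78) = 33.3%.
- Canagliflozin: 0.08/0.15 × (1 − e^−0.90) = 31.7%.
- Odds ratio: 0.463/0.500 = 0.93.
- SE of the difference: √[(0.333 × 0.667 + 0.317 × 0.683)/1,328] = 0.0182; expected z = 0.0168/0.0182 = 0.92.
- Two-sided rejection at nominal 5%: Φ(−1.96 + 0.92) + Φ(−1.96 − 0.92) = 15.0% + 0.2% = 15.2%.

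The same steps for the other settings:

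| Progression per year | Error, 0.5-point gap | Error, 1-point gap | Error, 2-point gap | Odds ratio, 2-point gap |
|---|---|---|---|---|
| 5% | 5.4% | 6.6% | 11% | 0.93 |
| 8% | 5.6% | 7.6% | 15% | 0.93 |
| 12% | 6.0% | 8.9% | 20% | 0.92 |

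With equal stopping the odds ratio is 1.00 and the error 5.0%. If placebo stops at 7% and canagliflozin at 5%, the odds ratio is 1.07 to 1.09 and false claims of benefit fall to 0.1-0.4%, below the nominal 2.5%.

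**Model 2: status read at the last on-treatment visit, with reversal at hazard g.**

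P = l/(l+g+d) × (1 − exp(−(l+g+d)T))

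For a 2-point gap and l from 5% to 12%, the error is 7-10% at g = 0.2 per year and 6-8% at g = 0.3 per year.

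**What removes the shift.** Over a common calendar window that includes off-drug ACR, both arms give 1 − exp(−lT); at l = 8% and T = 6.5 years that is 40.5% in each. In simulation (6.5 years, 1,443 per arm), a log-rank test of time to first progression, censored at drug stop, kept the error at 4.6-5.9% in every setting, including stopping of 5% against 7% or 8% per year.

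**The case against.** The strongest reply is that the vulnerable reading is inferred. Neither 9.5 nor 11.5.2 gives this endpoint a time point, 2.2.2 does not say each subject's own end of treatment, and 11.1 defers the ITT/mITT alignment to the SAP. A reader might infer that off-drug ACR is excluded; the protocol does not say so. This stands, and the point is therefore conditional. It does not clear the plan. Under mITT the data stop at last dose plus 30 days, so the problem is built in. Under ITT with off-drug ACR over a common window the shift largely disappears, but a logistic model without a time term still ignores unequal follow-up from death or withdrawn consent.

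The second reply concerns size. A 2-point gap on a 5% base is a 40% relative difference, while 1.1.2 calls the excess in discontinuations slight and their level generally low. ACR category can also fall back. Both stand, and they are why the smaller gaps and the reversible case are shown.

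A reader might also infer that placebo subjects would stop more because of poor glycaemic control. The protocol does not support this: 6.2.2 continues study drug after rescue, 6.2.1 provides for adjusting background therapy from Week 18, and the withdrawal criteria in 10.2 include no lack-of-efficacy criterion.

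Finally, the gate limits the harm. If canagliflozin has no effect on MACE, this test is seldom reached. If it has one, the protocol's own power for passing the gate is 33-76%.

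**Conclusion.** The concern holds in conditional form. The protocol fixes a binary proportion and a logistic model without time at risk, and ties the hypothesis to a treatment period whose length differs by subject. If the endpoint is read at each subject's own end of treatment, unequal stopping moves the odds ratio with no drug effect. More stopping on canagliflozin, the direction suggested by 1.1.2, would favour the drug.

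The size rests on assumed rates. It is negligible to modest for gaps of 0.5 to 1 point per year (error 5.4-8.9%). It becomes material at 2 points (11-20%, odds ratio 0.92-0.93), falling to about 6-10% if progression can reverse and status is read at the last visit. These errors apply to one dose tested at a nominal two-sided 5% once the gate has opened. It would be wrong to read them as the trial's family-wise error. The MACE analysis is unaffected. The change should be made, because the protocol already handles its primary endpoint this way and the ACR data needed are already scheduled.

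**What to change.** In 2.2.2 and 11.5.2, and correspondingly in the SAP:
- Define the endpoint as time from randomisation to first 1-step progression of albuminuria.
- Analyse it by a Cox or discrete-time model with the same terms, censoring at the last ACR.
- For the ITT estimate, use all scheduled ACR values, including posttreatment ones. Report data up to last dose plus 30 days as the on-treatment version.
- Keep the logistic proportion as a supportive analysis.

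The cost is wording; no new samples are needed. There are three downsides. Event times are known only to the visit interval, which a discrete-time model accommodates. A single transient crossing counts as an event unless confirmation on an existing repeat ACR is required. The ITT version includes off-drug time, and the on-treatment version assumes that stopping is unrelated to progression risk.

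If the endpoint is kept as a proportion, the minimum is to state the assessment window and whether off-drug ACR counts. That removes the ambiguity but leaves unequal follow-up from death or withdrawn consent unaddressed.

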11.5.3. Multiplicity Adjustment

To ensure the family-wise Type I error rate (alpha level) in this study is at most 5%, a gatekeeping procedure will be applied in testing the primary and secondary hypotheses. The superiority of the canagliflozin combined doses over placebo in time to MACE will be tested first. If statistically significant, the procedure will proceed to test the secondary endpoints of the proportion of subjects with progression of albuminuria and HOMA-B for

each canagliflozin dose versus placebo. Details of the gatekeeping procedure will be contained in the SAP.

11.5.4. Additional Secondary Efficacy Endpoints

Additional efficacy endpoints of interest will include the following:

- changes from baseline to end-of-treatment in the proinsulin/insulin ratio (in a subset of subjects), urinary albumin/creatinine ratio, and eGFR
- changes from baseline to Week 18 in HbA_{1c}, FPG, systolic and diastolic blood pressure, and body weight
- percent change from baseline to Week 18 in fasting plasma lipids (triglycerides, HDL-C, LDL-C, total cholesterol, and the ratio of LDL-C to HDL-C)

The continuous secondary efficacy endpoints, changes from baseline in the proinsulin/insulin ratio, HbA_{1c}, FPG, body weight, blood pressure, albuminuria, and eGFR and percent change in fasting lipids will be analyzed in the same manner as the secondary efficacy endpoint, change from baseline in HOMA-B.

For the assessment of change from baseline in HbA_{1c} at Week 18, subgroup analyses (described in detail in the SAP for this study) will be conducted to enhance understanding of factors that might impact glycemic response to canagliflozin.

11.6. Medical Resource Utilization Analyses

Medical Resource Utilization data analyses will be descriptively summarized by primary outcome variable (ie, those with a CV event versus those without) regardless of treatment group. These data may be used in future economic modeling to be done outside of the protocol.

11.7. Interim Analyses of CANVAS

11.7.1. Interim Analyses for Health Authority Submissions

Interim analyses of CANVAS will be done to prepare: (1) an interim safety report in support of the initial health authority filing, (2) the 18-week substudy reports, and (3) the CV safety meta-analyses (based on adjudicated data). The interim data from the CANVAS study will primarily supplement the safety and tolerability data generated from other studies in the canagliflozin development program.

11.8. Meta-Analysis to Support Regulatory Requirements

11.8.1. Meta-Analysis Pre-Regulatory Approval

To support submissions for marketing approval, the CV event data and other safety and efficacy results in this study will be exported and integrated with the data from other large, well-controlled, double-blind, randomized studies in the canagliflozin clinical development program. A meta-analysis of the integrated CV data will be conducted to compare canagliflozin with active or placebo control (eg, current FDA guidance requires

exclusion of the upper bound of the 2-sided 95% CI around the HR of 1.8 or greater). It is projected that the meta-analysis to support regulatory approval would be conducted when an approximate range of 140 to 160 composite events of MACE (CV death, nonfatal MI, nonfatal stroke) and hospitalized unstable angina are observed across the canagliflozin clinical development program (including CANVAS). In no case would a meta-analysis to support regulatory approval occur with fewer than 80 events. Note that the primary composite endpoint to show CV risk reduction in the present study includes MACE, while the pre-approval meta-analysis to rule out harm utilizes a composite endpoint that includes MACE plus hospitalized unstable angina.

If the meta-analysis occurs with 140 to 160 events, 30 to 40 are expected to be observed in the other large, well-controlled, double-blind, randomized studies that will be included in the meta-analysis and 110 to 120 observed from the CANVAS study.

Sponsor personnel will be unblinded to the data during the submission of data from this analysis; however, blinding to the subject's treatment allocation will be maintained for the subjects, investigators, Endpoint Adjudication Committee, and sponsor site-monitoring personnel throughout the study. In order to maintain data integrity with respect to endpoint adjudication, individuals within the sponsor responsible for submitting events to the Endpoint Adjudication Committee will handle the review and submission of adjudication packages in a completely blinded fashion.

The meta-analysis will be the subject of a separate SAP in which the objectives, hypotheses, and analytic strategy are described.

